#### **4.6.3 Study and Site Discontinuation**

The Sponsor has the right to terminate this study at any time. Reasons for terminating the study may include but are not limited to the following:

- The incidence or severity of adverse events in this or other studies indicates a potential health hazard to patients.
- Patient enrollment is unsatisfactory.

The Sponsor will notify the investigator if the Sponsor decides to discontinue the study.

The Sponsor has the right to close a site at any time. Reasons for closing a site may include but are not limited to the following:

- Excessively slow recruitment
- Poor protocol adherence
- Inaccurate or incomplete data recording
- Non-compliance with the International Council for Harmonisation (ICH) guideline for GCP
- No study activity (i.e., all patients have completed the study and all obligations have been fulfilled)

### **5. ASSESSMENT OF SAFETY**

#### **5.1 SAFETY PLAN**

The safety plan for patients in this study is based on clinical experience with obinutuzumab, *rituximab*, and idasanutlin in completed and ongoing studies. The anticipated important safety risks of obinutuzumab, *rituximab*, and *idasanutlin* are outlined below. Refer to the Obinutuzumab, *Rituximab*, and Idasanutlin Investigator's Brochures for a complete summary of safety information and prescribing information.

Several measures will be taken to ensure the safety of patients participating in this study. Eligibility criteria have been designed to exclude patients at higher risk for toxicities (see Section 4.1). In addition, patients will undergo adequate safety monitoring during the study, as described in this section and in Section 4.5. Guidelines for managing adverse

events, including criteria for dosage modification and treatment delays or discontinuation, are provided in Section 5.1.5.

### **5.1.1 Risks Associated with Obinutuzumab**

As of 4 July 2016, the following adverse events are considered to be important risks associated with obinutuzumab: IRRs, TLS, thrombocytopenia (including acute thrombocytopenia), neutropenia (including prolonged and late onset neutropenia), infections (including PML and HBV reactivation), prolonged B-cell depletion, impaired immunization response worsening of preexisting cardiac conditions, gastrointestinal perforation, immunogenicity, and second malignancies. *These events, with the exception of prolonged B-cell depletion, immunogenicity, and second malignancies, are described below.*

#### **5.1.1.1 Infusion-Related Reactions**

IRRs have been reported predominantly during the first infusion of obinutuzumab. The incidence and severity of IRRs decreased substantially with the second and subsequent infusions. In the majority of patients, IRRs were mild or moderate and resolved with the slowing or interruption of the infusion and supportive care. Commonly experienced IRRs have been characterized by hypotension, fever, chills, flushing, nausea, vomiting, hypertension, fatigue, and other symptoms.

IRRs may be clinically indistinguishable from IgE-mediated allergic or anaphylactic reactions; anaphylaxis has been reported in patients treated with obinutuzumab.

Hypotension may occur during obinutuzumab IV infusions. Therefore, withholding of anti-hypertensive treatments should be considered for 12 hours prior to and throughout each obinutuzumab infusion and for the first hour after administration. Patients at acute risk of hypertensive crisis should be evaluated for the benefits and risks of withholding their anti-hypertensive medication.

Patients who have preexisting cardiac or pulmonary conditions should be monitored carefully throughout the infusion and the post-infusion period.

Guidelines for medical management of IRRs and anaphylaxis are provided in Section 4.3.2.1 and Appendix 9.

#### **5.1.1.2 Tumor Lysis Syndrome**

TLS, including fatal events, has been reported with obinutuzumab administration. Patients at risk for TLS (e.g., because of bulky disease or renal insufficiency) should receive adequate hydration and premedication with allopurinol or an alternative uricostatic agent as indicated in Section 4.3.2.6 (see Table 9). Additional guidelines for management of TLS in this study are provided in Section 5.1.5.

### **5.1.1.3 Neutropenia**

Grade 3 or 4 neutropenia, including febrile neutropenia, has been reported with obinutuzumab administration. Neutropenia resolved spontaneously or with use of hematopoietic growth factors. Patients who experience Grade 3 or 4 neutropenia should be closely monitored until neutrophil values return to at least Grade 2. Cases of late-onset neutropenia (ANC < 1000 cells/ $\cdot$ L occurring  $\cdot$  28 days after obinutuzumab treatment has been completed or stopped) or prolonged neutropenia (ANC < 1000 cells/ $\cdot$ L that does not resolve after 28 days without obinutuzumab treatment) have also been reported. Prophylactic treatment with antibiotics should be administered as per standard practice. The use of G-CSF is allowed for treatment of neutropenia in this study. Guidelines for primary prophylaxis with G-CSF are provided in Section 4.4.1.

### **5.1.1.4 Thrombocytopenia**

Severe and life-threatening thrombocytopenia, including acute thrombocytopenia (occurring within 24 hours after the infusion), has been observed during treatment with obinutuzumab. In patients with CLL exposed to obinutuzumab, fatal hemorrhagic events have also been reported in Cycle 1. A clear relationship between thrombocytopenia and hemorrhagic events has not been established. Patients should be closely monitored for thrombocytopenia, especially during the first cycle of treatment. For patients who experience thrombocytopenia, regular laboratory tests should be performed until the event resolves, and dose delays should be considered in case of severe or life-threatening thrombocytopenia. Transfusion of blood products (i.e., platelet transfusion) may be performed at the discretion of the treating physician, according to institutional practice.

### **5.1.1.5 Infections**

On the basis of its mechanism of action, resulting in profound B-cell depletion, obinutuzumab may be associated with an increased risk of infections. Obinutuzumab should not be administered to patients with active infection, and caution should be exercised when including patients with a history of recurrent or chronic infections.

Serious bacterial, fungal, and new or reactivated viral infections can occur during and following the completion of obinutuzumab therapy. Fatal infections have been reported.

Reactivation of hepatitis B in patients with chronic hepatitis (HBsAg positive), with evidence of prior hepatitis B exposure (HBsAg negative and HBcAb positive), or in patients who are carriers has been reported with other anti-CD20 antibodies. The risk is increased particularly when anti-CD20 antibodies are administered with immunosuppressive therapies, such as steroids or chemotherapy. Particular attention should be given to patients who have previously received highly immunosuppressive treatment, such as high-dose chemotherapy and SCT. Patients who are positive for HBsAg and HBcAb are not eligible for enrollment in this study.

John Cunningham (JC) viral infection resulting in PML has been reported in patients treated with obinutuzumab. The diagnosis of PML should be considered in any patient presenting with new-onset neurologic manifestations. The symptoms of PML are unspecific and can vary depending on the affected region of the brain. Motor symptoms with corticospinal tract findings (e.g., muscular weakness, paralysis, and sensory disturbances), sensory abnormalities, cerebellar symptoms, and visual field defects are common. Some signs or symptoms regarded as "cortical" (e.g., aphasia or visual-spatial disorientation) may occur. Evaluation of PML includes but is not limited to consultation with a neurologist, brain MRI, and lumbar puncture (cerebrospinal fluid testing for JC viral DNA). Additional guidelines for medical management of PML in this study are provided in Section 5.1.2.

#### **5.1.1.6 Immunizations**

The safety of immunization with live virus vaccines following obinutuzumab therapy has not been studied. Thus, vaccination with live virus vaccines is not recommended during treatment and until B-cell recovery.

#### **5.1.1.7 Worsening of Preexisting Cardiac Condition**

In patients with underlying cardiac disease and treated with obinutuzumab, adverse events such as angina pectoris, acute coronary syndrome, myocardial infarction, heart failure, and arrhythmias, including atrial fibrillation and tachyarrhythmia, have been observed. These events may occur as part of an IRR and can be fatal. Therefore, patients with a history of cardiac disease should be monitored closely. In addition, these patients should be hydrated with caution to prevent a potential fluid overload.

#### **5.1.1.8 Gastrointestinal Perforation**

GI perforation has been reported in patients with NHL treated with obinutuzumab, including fatal events. Patients with GI involvement should be monitored for signs of GI perforation.

### **5.1.2 Risks Associated with Rituximab**

*The following adverse events are considered to be important risks associated or potentially associated with rituximab: IRRs, infections (including severe infections), PML, hepatitis B reactivation, neutropenia (including prolonged neutropenia), TLS, impaired immunization response, severe skin reactions (Stevens-Johnson syndrome/toxic epidermal necrolysis), and GI perforation. Details for these risks are provided below; refer to the Rituximab Investigator's Brochure for full information.*

#### **5.1.2.1 Infusion-Related Reactions**

*Acute IRRs are very common in patients receiving rituximab (occurring in • 10% of patients) based on clinical trial experience. However, serious IRRs are uncommonly reported (occurring in • 1 of 1,000 and < 1 of 100 patients) and are rarely fatal (occurring in • 1 of 10,000 and < 1 of 1,000 patients). Most IRRs occur with the first administration of rituximab. Most IRRs are mild to moderate in severity (Grade 1/2)*

and can be managed by slowing or stopping the rituximab infusion. IRRs can be severe and in rare cases can result in death. Rituximab-induced IRRs consist of a cluster of symptoms and signs occurring during or within 24 hours of a rituximab infusion, which may be related to cytokine release and/or other chemical mediators, and these acute IRRs overlap with “cytokine release syndrome.” Anaphylactic and other hypersensitivity reactions have been reported following rituximab administration, and clinical manifestations of these reactions are similar to cytokine release syndrome. In contrast to cytokine release syndrome, true hypersensitivity reactions typically occur within minutes of starting the rituximab infusion.

#### **5.1.2.2 Infections (Including Serious Infections)**

Serious infections, including fatal bacterial, fungal, and new or reactivated viral infections, can occur during and up to 1 year following completion of rituximab-based therapy.

#### **5.1.2.3 Hepatitis B Reactivation**

Reactivation of hepatitis B ranges from asymptomatic reactivations (detected by changes in laboratory parameters only) to fulminant liver failure and death. Patients with chronic hepatitis B (HBsAg positive) viral infection are at risk for reactivation and will be excluded from the study. Patients with evidence of prior hepatitis B exposure or who are carriers (defined as HBsAg negative and anti-HBcAb positive) are at a lower risk for reactivation. Patients who demonstrate evidence of reactivation while receiving an appropriate anti-viral therapy will be discontinued from study treatment.

#### **5.1.2.4 Progressive Multifocal Leukoencephalopathy**

Rare cases of PML have also been reported in patients treated with rituximab alone or in combination with other immunosuppressive medications (Goldberg et al. 2002; Calabrese et al. 2007; Carson and Bennett 2009). In a review of 57 patients who developed PML after rituximab administration, all patients had received prior therapies with alkylating agents, corticosteroids, purine analogs, or drugs to prevent allogeneic stem cell or solid-organ graft rejection. The diagnosis of PML in any patient treated with rituximab is rare, but it should be suspected in any patient who develops new-onset neurologic manifestations. The majority of patients with hematologic malignancies diagnosed with PML received rituximab in combination with chemotherapy or as part of a hematopoietic SCT. Most cases of PML were diagnosed within 12 months of the patients' last infusion of rituximab.

#### **5.1.2.5 Neutropenia (Including Prolonged Neutropenia)**

Neutropenia is very common in patients receiving rituximab (occurring in • 10% of patients) based on clinical trial experience. However, delayed onset neutropenia is very rare (occurring in < 1 of 10,000 patients), and the incidence of prolonged neutropenia is unknown. Neutropenia may lead to serious or overwhelming infection, especially if profound (Grades 3•4), prolonged, associated with breaches in natural mucosal barriers

(e.g., diarrhea and/or mucositis), and/or other immunological defects (e.g., lymphopenia, hypogammaglobulinemia, and acquired immunodeficiency syndrome). Despite an increase in incidence of neutropenia and Grade 3•4 neutropenia associated with rituximab, most studies have not reported a significant increase in serious neutropenic infections.

#### **5.1.2.6 Tumor Lysis Syndrome**

Patients treated with rituximab may be at risk for TLS. Severe TLS is very rare in patients receiving rituximab (occurring in < 1 of 10,000 patients), based on postmarketing experience. Signs and symptoms (e.g., hyperuricemia, hyperkalemia, hypocalcemia, hyperphosphatemia, acute renal failure, and elevated LDH) that are consistent with TLS have been reported to occur after the first rituximab IV infusion in patients with high numbers of circulating malignant lymphocytes. A high number of circulating malignant cells ( $\bullet$  25,000/mm^3) or high tumor burden confers a greater risk of TLS. For patients with evidence of TLS, rituximab should be discontinued, and the patient should be treated as clinically indicated.

#### **5.1.2.7 Impaired Immunization Response**

B-cell depletion is expected (and desired) during rituximab therapy and is directly related to its mechanism of action. In theory, peripheral B-cell depletion may reduce the effectiveness of immunization, since patients may not be able to mount an effective humoral immune response to foreign antigens.

#### **5.1.2.8 Stevens Johnson Syndrome and Toxic Epidermal Necrolysis**

Severe reactions, including fatal mucocutaneous reactions, can occur in patients receiving rituximab. The onset of these reactions in patients treated with rituximab has varied from 1 to 13 weeks following rituximab exposure. The majority of the TEN/SJS cases reported with rituximab were associated with additional risk factors. Fatal outcome also appeared to increase in patients who were exposed to multiple risk factors for TEN/SJS.

#### **5.1.2.9 Gastrointestinal Perforation**

Abdominal pain, bowel obstruction, and perforation, in some cases leading to death, can occur in patients receiving rituximab in combination with chemotherapy. In postmarketing reports of rituximab, the mean time to documented GI perforation was 6 days (range: 1•77 days) in patients with NHL.

### **5.1.3 Risks Associated with Idasanutlin**

Information related to idasanutlin-associated risks is based mainly on review of data from Phase I experience in patients with solid tumors and AML (Studies NP27872, NP28902, and NP28679, respectively) as described in the Idasanutlin Investigator's Brochure. In Study NP27872 and NP28902, 160 patients with advanced malignancies (excluding leukemia) have received idasanutlin in the Phase I, entry-into-human, dose-escalation study NP27872 (99 patients) and in the Phase I DDI and relative

bioavailability study NP28902 (61 patients). Study BH29812 (idasanutlin plus obinutuzumab in R/R FL and DLBCL) had enrolled 1 patient as of 1 May 2016.

*Many of the toxicities experienced by patients with solid tumors appear to be manageable with appropriate prophylaxis, supportive therapies, and/or reversible with discontinuation of idasanutlin. Identified risks include GI disorders (diarrhea, nausea, and vomiting, myelosuppression (thrombocytopenia, neutropenia, and anemia), TLS, infectious complications, and electrolyte abnormalities. Potential risks include coagulation abnormalities and liver function test abnormalities.*

*Please refer to the current version of the Idasanutlin Investigator's Brochure for additional information on the identified and potential risks.*

#### **5.1.3.1 Gastrointestinal Disorders**

*The adverse GI events in the Phase I idasanutlin studies include primarily diarrhea, nausea, vomiting, and anorexia. Diarrhea is the most common adverse event observed across treatment groups and indications. It has been reported in a large majority of patients treated with idasanutlin and rarely presented as severe. Nausea and vomiting have also been reported during clinical experience with idasanutlin. Clinical monitoring for potential complications is required. Patients who develop GI disorders should have other or concomitant causes ruled out. Appropriate event management and prophylaxis should be considered.*

#### **5.1.3.2 Myelosuppression**

*Idasanutlin was associated with myelosuppression (thrombocytopenia, neutropenia, anemia, and aplasia) in Study NP27872, evaluating idasanutlin in patients with solid tumors.*

#### **Thrombocytopenia**

*MDM2 antagonists were shown in vitro to affect all types of hematopoietic progenitors, including megakaryocytic differentiation. They inhibit both early and late stages of megakaryopoiesis, including ploidy and proplatelet formation (Mahfoudhi et al. 2016). As a consequence, the effect on early progenitors might induce long-lasting thrombocytopenia in vivo. Clinical data on the severity and duration of thrombocytopenia with idasanutlin are limited. Study NP27872, evaluating idasanutlin in patients with solid tumors, has shown possible exposure-dependent thrombocytopenia with an association between AUC/cycle and platelet nadir of the first cycle treatment for the daily dosing schedule, together with AUC/cycle as a determinant for Grade • 4 thrombocytopenia. The potential relation between thrombocytopenia and hemorrhagic events has not been confirmed.*

### ***Neutropenia and Febrile Neutropenia***

*In Study NP27872, a possible exposure-dependent neutropenia was shown, with AUC/cycle as a determinant for Grade 4 neutropenia within the first two cycles in the daily schedule.*

*Blood counts will be monitored closely throughout study treatment (see the schedules of activities in [Appendix 1](#) and [Appendix 2](#)); a Grade • 3 decrease in neutrophil levels should be followed until resolution (to Grade • 2 or baseline value) and additional measures considered as clinically indicated (see [Section 5.1.5](#)). Use of hematopoietic growth factors is encouraged during study treatment, particularly for patients who experience a first event of Grade • 3 neutropenia during the study treatment phase.*

#### **5.1.3.3 Infections**

*Infections of various etiologies (including infections with fatal outcome) have been reported in patients treated with idasanutlin, primarily in patients with AML. The disease under study itself is associated with impaired immune function and increased susceptibility to infections. Assessment of causality for these cases can be difficult, and it is unclear whether or how much the incidence could be increased due to idasanutlin treatment. Because of the potential of idasanutlin to induce myelosuppression, patients should be carefully screened for evidence of active or uncontrolled infection or other uncontrolled disorder prior to enrollment. Patients in this study will be closely monitored for infection, and prompt therapy will be instituted as necessary. In any patient with uncontrolled and/or severe diarrhea, the presence of *Clostridium difficile* infection should be investigated.*

#### **5.1.3.4 Tumor Lysis Syndrome**

*There is a potential for TLS in patients treated with idasanutlin. Laboratory evidence of TLS has been reported for patients with AML treated in Study NP28679 and in patients considered to be at high risk of TLS owing to initial high WBC count. Clinical features were rare. For TLS-specific management and recommendations, refer to [Section 5.1.5](#).*

#### **5.1.3.5 Electrolyte Disorders**

*Electrolyte disorders (hypercalcemia, hyperkalemia, hyponatremia, hypocalcaemia, hypokalemia, hypomagnesemia, hyponatremia, hyperphosphatemia, and hypophosphatemia) were commonly observed in patients treated with idasanutlin. In addition to institutional guidelines, electrolytes should be monitored during the treatment phase. Electrolyte disorders should be treated according to institutional guidelines.*

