### **1.3.3 Clinical Studies with RO5045337 and Idasanutlin**

Initial proof of mechanism for MDM2 inhibition leading to p53 activation was demonstrated in solid tumors with RO50405337; however, best response observed in relapsed solid tumor patients was stable disease (SD) (RO5045337 Investigator's Brochure).

In the RO5045337 leukemia study (NO21279), 96 patients relapsed or refractory to all available standard-of-care regimens were treated in stratum A (AML, ALL, and CML) and 20 patients in stratum B (CLL) during dose escalation. The doses ranged from 20 mg/m^2 to 1920 mg/m^2. One patient achieved a PR (and continued to receive 25 cycles; the patient had a history of [REDACTED]), and 15 patients showed SD with this early formulation of the MDM2-inhibitor (RO5045337).

Six patients experienced at least one Grade 4 adverse event. Grade 4 adverse events in patients with CLL included pneumonia, hypophosphatemia, febrile neutropenia, and hemorrhagic stroke (reported in 1 patient each) and anemia and thrombocytopenia (in 2 patients each). The events were considered by the investigator to be study treatment related. The patients received treatment for the adverse event and continued study treatment without dose adjustments. No dose-limiting toxicities (DLTs) were reported in 20 patients with CLL.

*As of 13 September 2016, idasanutlin had been studied in 298 patients in the Phase I/II program, including 131 patients with AML (and 1 patient with CML), 160 patients in the solid tumor setting, and 6 patients with NHL.*

The idasanutlin solid tumor study (NP27872; n=99) tested different doses and schedules using the MBP formulation. The study was an entry-into-human, multiple-ascending dose-escalation study with two dosing schedules (weekly • 3 [Schedule A] vs. daily [• 5

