## **4.5.6 Laboratory, Biomarker, and Other Biological Samples**

### **4.5.6.1 Local Laboratory Assessments**

Samples for the following laboratory tests will be analyzed at the study site's local laboratory for analysis:

- Hematology: hemoglobin, hematocrit, platelet count, RBC count, WBC count, percent or absolute WBC differential count (neutrophils, eosinophils, basophils, monocytes, lymphocytes, and other cells)
- Serum chemistry: sodium, potassium, glucose, BUN or urea, creatinine, calculated creatinine clearance, calcium, total bilirubin, direct bilirubin, total protein, albumin, ALT, AST, alkaline phosphatase, amylase, lipase, LDH, and uric acid
- $\alpha_2$  microglobulin
- Coagulation: INR, aPTT (or PTT), and PT
- Pregnancy test
  - All women of childbearing potential will have a serum pregnancy test at screening (within 7 days of Day 1 of Cycle 1). Because of the suspected effect of idasanutlin on embryo-fetal development, monthly pregnancy testing is strongly recommended for women of childbearing potential ([CTFG 2014](#))
- Viral serology
  - Hepatitis B testing includes HBsAg and total HBcAb.
  - Hepatitis C testing includes HCV antibody.
- Quantitative immunoglobulins: IgA, IgG, and IgM
- *Bone marrow assessment*

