### **5.2.3 Adverse Events of Special Interest (Immediately Reportable to the Sponsor)**

Adverse events of special interest are required to be reported by the investigator to the Sponsor immediately (i.e., no more than 24 hours after learning of the event; see Section 5.4.2 for reporting instructions). Adverse events of special interest for this study include the following:

- Cases of potential drug-induced liver injury that include an elevated ALT or AST in combination with either an elevated bilirubin or clinical jaundice, as defined by Hy's Law (see Section 5.3.5.7)
- Suspected transmission of an infectious agent by study treatment, as defined below  
Any organism, virus, or infectious particle (e.g., prion protein transmitting transmissible spongiform encephalopathy), pathogenic or non-pathogenic, is considered an infectious agent. A transmission of an infectious agent may be suspected from clinical symptoms or laboratory findings that indicate an infection in a patient exposed to a medicinal product. This term applies only when a contamination of any of the study treatment components is suspected.
- TLS of any grade, irrespective of causality
- Grade • 3 neutropenia, including febrile neutropenia
- Grade • 2 diarrhea
- Grade • 3 thrombocytopenia or Grade 2 thrombocytopenia if associated with hemorrhage/bleeding
- *Grade • 2 Clostridium difficile infection*
- *Second malignancies*

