### Schedule of Activities for Patients with Follicular Lymphoma (Dose-Escalation and Expansion) (cont.)

- m Unexplained fever > 38°C, nightsweats, unexplained weight loss > 10% of body weight over 6 months.
- n Includes hemoglobin, hematocrit, platelet count, RBC count, WBC count, and percent or absolute WBC differential count (neutrophils, eosinophils, basophils, monocytes, lymphocytes, other cells).
- o Screening laboratory assessments may be used for Day 1 of Cycle 1 if performed within 72 hours prior to Day 1 of Cycle 1.
- p Perform hematology and chemistry tests within 72 hours prior to Day 1 of each cycle and within 24 hours prior to Days 8 and 15 of Cycle 1. Samples for exploratory biomarker research should be collected at the same time as hematology and chemistry samples.
- q Includes sodium, potassium, glucose, BUN or urea, creatinine, calculated creatinine clearance, calcium, total bilirubin, direct bilirubin, total protein, albumin, ALT, AST, alkaline phosphatase, amylase, lipase, LDH, and uric acid.
- r All women who are not postmenopausal (• 12 months of non-therapy-induced amenorrhea) or surgically sterile will have a serum pregnancy test at screening within 7 days prior to Day 1 of Cycle 1. Because of the suspected effect of idasanutlin on embryo-fetal development, monthly pregnancy testing is strongly recommended for women of childbearing potential ([CTFG 2014](#)).
- s Includes hepatitis B surface antigen, total hepatitis B core antibody, and hepatitis C virus antibody.
- t Perform at the same time as tumor assessments at 12, 18, and 24 months after initiation of induction treatment.
- u Perform every 3 months until recovery to either normal range or baseline level, disease progression, or the start of new anti-lymphoma treatment, whichever occurs first.
- v See [Appendix 3](#) and [Appendix 4](#) for detailed schedule.
- w Includes circulating lymphoma cells and/or cell-free circulating tumor DNA.
- x Includes B-cell counts (CD19), T-cell counts (CD3, CD4, and CD8), and NK-cell counts (CD16 and CD56).
- y Also on Day 5 of this cycle. See [Appendix 3](#) and [Appendix 4](#) for detailed schedule.
- z Cycle 4 Day 1 and Day 5. See [Appendix 3](#) and [Appendix 4](#) for detailed schedule.

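### The scheduled chemistry panel omits magnesium and phosphate, although the protocol names their disorders as common with idasanutlin and makes TLS of any grade an event of special interest

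*Combined protocol and SAP*

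**What the plan says.** Section 5.1.3.5 identifies disorders of calcium, potassium, sodium, magnesium and phosphate as frequent with idasanutlin; its list closes with "hypomagnesemia, hyponatremia, hyperphosphatemia, and hypophosphatemia) were commonly observed in patients treated with idasanutlin". It then directs: "In addition to institutional guidelines, electrolytes should be monitored during the treatment phase". It names no analytes, timepoints or frequency.

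Section 5.2.3 makes "TLS of any grade, irrespective of causality" an adverse event of special interest. Section 5.1.2.6, in the rituximab risks, gives the signs of tumor lysis syndrome (TLS) as "hyperuricemia, hyperkalemia, hypocalcemia, hyperphosphatemia, acute renal failure, and elevated LDH". Section 5.1.3.4 adds that TLS with idasanutlin in AML showed mainly in laboratory results, with clinical features rare.

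Section 4.5.6.1 defines the panel as "Serum chemistry: sodium, potassium, glucose, BUN or urea, creatinine, calculated creatinine clearance, calcium, total bilirubin, direct bilirubin, total protein, albumin", followed by liver and pancreatic enzymes, LDH and uric acid. Appendix 1 footnote q repeats it: "Includes sodium, potassium, glucose, BUN or urea, creatinine, calculated creatinine clearance, calcium, total bilirubin, direct bilirubin, total protein, albumin", with the same remainder. Appendix 2 footnote s is the same.

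Changes in laboratory results are a safety endpoint (Section 2.1) and are to be summarized as change from baseline (Section 6.3).

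**The concern.** The protocol's risk statement and its data collection do not match. A site can run every scheduled chemistry panel and still have no magnesium or phosphate value for any patient, although the protocol names disorders of both as common effects of the drug under study.

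Two things are at stake. The first is the laboratory safety summary, which can describe only what was measured; for these two analytes it would be empty or would hold whatever individual sites chose to add. The second is consistency of event capture across about 25 sites. An asymptomatic low magnesium or abnormal phosphate can be recorded only if someone orders the test. Where that is left to local interpretation of a general instruction, identical patients can be recorded differently. During dose escalation the same unevenness could reach the toxicity count that drives the dose model.

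**Working it through.** The plan states no figure on this point, and no sample-size or error-rate formula applies. The check compares lists and then follows the route from a laboratory value to a recorded event.

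**1. The panel.** Section 4.5.6.1, Appendix 1 footnote q and Appendix 2 footnote s give the same 18 items. The electrolytes among them are sodium, potassium and calcium. Alkaline phosphatase is on the list, but it is an enzyme and does not measure phosphate.

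**2. Electrolyte disorders in Section 5.1.3.5 against the panel.**

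| Named disorder | Scheduled analyte |
|---|---|
| Hypercalcemia, hypocalcemia | Calcium |
| Hyperkalemia, hypokalemia | Potassium |
| Hyponatremia (printed twice) | Sodium |
| Hypomagnesemia | None |
| Hyperphosphatemia | None |
| Hypophosphatemia | None |

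As printed there are 8 distinct disorders: 8 − 3 = 5 are covered and 3 are not. The amendment summary for the same section has hypernatremia where the current text first prints hyponatremia. If that is what was meant, there are 9 disorders: 9 − 3 = 6 covered and 3 not. The uncovered three are the same either way.

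**3. TLS signs in Section 5.1.2.6 against the panel.**

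| Sign | Scheduled analyte |
|---|---|
| Hyperuricemia | Uric acid |
| Hyperkalemia | Potassium |
| Hypocalcemia | Calcium |
| Hyperphosphatemia | None |
| Acute renal failure | Creatinine |
| Elevated LDH | LDH |

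6 − 1 = 5 are covered and one is not.

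**4. Other scheduled tests.** The remaining laboratory tests are hematology, coagulation, β2 microglobulin, pregnancy test, viral serology, immunoglobulins, bone marrow, drug concentrations and biomarkers. None yields magnesium or phosphate.

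**5. Unscheduled routes.** There are four: the general instruction in Section 5.1.3.5; close electrolyte monitoring once diarrhea is being managed (Table 19); electrolyte correction once TLS is recognized (Table 19); and a search for risk factors, electrolytes among them, after QTcF prolongation (Section 4.5.7). None names magnesium or phosphate, and none sets a routine timepoint. Three of the four start only after another event.

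**6. From value to event.** Under Section 5.3.5.5 an abnormal result must be reported as an adverse event if it comes with symptoms, changes study treatment, leads to a medical intervention or change in concomitant therapy, or is judged clinically significant. Under Section 3.1.2.1 a Grade 3 or 4 non-hematologic adverse event in the assessment window is dose-limiting if the investigator does not consider it clearly related to the lymphoma. The listed exceptions (infusion reactions, certain diarrhea, nausea or vomiting) do not include electrolyte events. A symptomatic patient can be investigated under any panel. The exposed group is therefore asymptomatic patients whose value, had it been seen, would have been treated or judged significant.

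**The case against.** The best case for the plan is that it already tells sites to monitor electrolytes, in the same paragraph that names these disorders. It also asks for electrolyte checks or correction in diarrhea and TLS, and measures five of the six TLS signs. That stands, and it limits the point to unnamed analytes and unset timepoints. It does not close the gap, because two sites can read the instruction differently and both comply.

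Several stronger readings are tempting, and the documents do not support them.

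- A reader might infer that these disorders will be seen only where a site happens to test as a matter of routine. Section 5.1.3.5 does instruct monitoring; what it lacks is specificity.
- A reader might infer that any Grade 3 or 4 magnesium or phosphate value is a dose-limiting toxicity. It must first qualify as an adverse event, and Section 5.3.5.5 notes that some abnormal values in oncology studies may not.
- Section 1.3.3 reports "Grade 4 adverse events in patients with CLL included pneumonia, hypophosphatemia, febrile neutropenia, and hemorrhagic stroke", which might be taken as direct evidence. Those patients received the predecessor compound RO5045337; the hypophosphatemia was in one patient. They continued without dose adjustment, and no dose-limiting toxicity was reported in the 20 CLL patients.
- One might size the gap by multiplying chemistry draws by total enrolment. An obinutuzumab patient has 3 + 2 + 4 × 2 = 13 induction draws. A rituximab patient has 2 + 1 + 4 = 7, because Appendix 2 footnote t restricts Day 15 chemistry to patients given obinutuzumab. The dose-finding argument concerns at most 40 patients in any case.
- An extra chemistry panel on Day 5 might seem to follow. No section calls for chemistry between Days 1 and 8, and Regimen B has no Cycle 1 Day 5 concentration sample to attach it to. It is a separate design preference.

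**Conclusion.** The mismatch is real and is the same in all three places that define the panel. Three named electrolyte disorders and one of six listed TLS signs have no scheduled measurement, so the laboratory-change endpoint cannot describe them and capture of asymptomatic cases may differ by site. TLS as a whole is not invisible; only its phosphate component is unmeasured.

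The effect on dose escalation cannot be estimated, because the documents give no frequency for Grade 3 or 4 magnesium or phosphate events with idasanutlin. The direction is clear: an undetected event can only lower the toxicity count. Section 3.1.2.3 shows what a single count can do. After a clean 100 mg cohort, no toxicity in three patients at 250 mg leads to a 300 mg recommendation, and one toxicity leads to 250 mg. A reader might infer from this that the recommended dose will be biased upward. The example shows a consequence and not a frequency, and the same section lets clinical judgment override the model.

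The conclusion assumes that the three printed lists are complete and that sites are not otherwise required, for instance by a laboratory manual, to measure the two analytes.

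**What to change.** Reconcile Section 5.1.3.5 with the panel by adding magnesium and phosphate to the serum chemistry list in Section 4.5.6.1, Appendix 1 footnote q and Appendix 2 footnote s. Both would run on draws already scheduled, so no visit or additional sampling timepoint is needed. Scheduled coverage would become complete for the named electrolyte disorders (8 of 8 as printed, or 9 of 9) and for the listed TLS signs (6 of 6). The repeated hyponatremia entry in Section 5.1.3.5 should be checked in the same amendment.

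The cost is two routine local analytes per chemistry draw, edits to three lists, and a few more asymptomatic laboratory events recorded. No sample size, analysis method or treatment rule changes.
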